#### 6.3 Trial Participants

#### 6.3.1 Overall Description of Trial Participants

Inclusion criteria are pregnant woman from 30 weeks of pregnancy. With no concerns raised regarding the pregnancy prior to this gestation and a body mass index (BMI) at booking of 18-30.

#### 6.3.2

#### Inclusion Criteria

- Participant is willing and able to give informed consent for participation in the study.
- Female, aged 18-40 years.
- To start study prior to 32 weeks of pregnancy
- BMI 18-30 at booking
- Able (in the Investigators opinion) and willing to comply with all study requirements.
- Willing to allow her General Practitioner and Obstetric Consultant, to be notified of participation in the study.
- Singleton pregnancy

CONFIDENTIAL

Formatted: Not Highlight

Formatted: Superscript, Not Highlight

Formatted: Superscript, Not Highlight

Formatted: Not Highlight

#### **Exclusion Criteria**

- If any concerns have been raised at previous scans, although if the scan has been reviewed by fetal medicine and deemed there are no concerns then the patient can be included
- A delivery planned prior to 39 weeks at recruitment.
- Multiple pregnancy.

#### 6.4Study Procedures

#### 6.4.1 Informed Consent

The participant must personally sign and date the latest approved version of the informed consent form before any study specific procedures are performed.

Written and verbal versions of the participant information and Informed consent will be presented to the participants detailing no less than: the exact nature of the study; the implications and constraints of the protocol; the known side effects and any risks involved in taking part. It will be clearly stated that the participant is free to withdraw from the study at any time for any reason without prejudice to future care, and with no obligation to give the reason for withdrawal.

The participant will be allowed as much time as wished to consider the information, and the opportunity to question the Investigator, their GP or other independent parties to decide whether they will participate in the study. Written Informed Consent will then be obtained by means of participant dated signature and dated signature of the person who presented and obtained the informed consent. The person who obtained the consent must be suitably qualified and experienced, and have been authorised to do so by the Chief/Principal Investigator. A copy of the signed Informed Consent will be given to the participants. The original signed form will be retained at the study site.

## 6.4.2 Screening and Eligibility Assessment

Participants will be approached at 20 week scan, attendance at outpatient clinic or day assessment unit between 20-30 weeks. Then given a patient information leaflet and asked whether they would be happy to have a follow up phone call for screening and to see whether they would like to participate and be invited back for potential participation. The study will also be publicised within the Rosie and on the Rosie social media pages. Patients will also be able to contact the WOMB team to enquire about the study and enrolment.

#### Demographics

The date of birth, parity, gestation at first contact, estimated delivery date, body mass index at

CONFIDENTIAL

Page 11 of 29

Version 2 April 12th 2021

Formatted: Superscript, Not Highlight

Formatted: Not Highlight

Formatted: Not Highlight

booking of pregnancy will be recorded.

Medical history

Plans to delivery prior to 39 week will be noted and the woman not eligible.

#### 6.4.3 Baseline Assessments

Body mass index to be completed if not done at booking.

#### 6.4.5 Subsequent assessments

The assessment of the patient will involve four twenty minute scans at 32,34,36 and 38 weeks. Where movements noted by mother, scan operator and device will be recorded separately. We would aim for these to be in 32nd, 34th, 36th, 38th week. For example, week 32 ±1 week, week 34 ±1 week, week 36 ±1 week, and week 38 ±1 week..The scans would take place ideally every 14 days but it would be acceptable with a 10-18 days gap. This allows for patient convenience. Summary of visits in Appendix 1.

#### 6.5 Definition of End of Trial

The end of trial is the date of the last visit/ telephone follow up/ home visit of the last participant. The last phone call will occur at 8 weeks post natal.

## 6.6 Discontinuation/Withdrawal of Participants from Study Treatment

Each participant has the right to withdraw study at any time. In addition, the investigator may discontinue a participant from the study at any time if the investigator considers it necessary for any reason including:

- Significant protocol deviation
- If the patient gives birth prior to the completion of the scan protocol. We will use
  the data from the scans up until that point and record they delivered prior to all
  scans being complete.
- Ineligibility (either arising during the study or retrospective having been overlooked at screening)
- Significant non-compliance with treatment regimen or study requirements
- An adverse event which requires discontinuation of the study or results in inability to continue to comply with study procedures
- · Consent withdrawn
- Lost to follow up

CONFIDENTIAL

Page 12 of 29

Formatted: Superscript, Not Highlight

Formatted: Not Highlight

The reason for withdrawal will be recorded in the CRF.

If the participant is withdrawn due to an adverse event, the investigator will arrange for followup visits or telephone calls until the adverse event has resolved or stabilised.

#### 6.7 Source Data

Medical records at Cambridge university hospital are on EPIC a computerised medial note system. These include, but are not limited to, hospital records (from which medical history and previous and concurrent medication may be summarised into the CRF).

All documents will be stored safely in confidential conditions. On all study-specific documents, other than the signed consent, the participant will be referred to by the study participant number/code, not by name.

#### 7 TREATMENT OF TRIAL PARTICIPANTS

#### 7.1 Description of Study Intervention(s)

The study intervention will involve four ultrasound scans lasting 20 mins during which fetal movements will be recorded. The fabric device will also be worn on the mother's abdomen and will also be recording movement. The mother will also have a button to press when she feels movements.

## 7.2 Maintenance and storage of device

The device will be in two parts. The fabric wearable part and a separate recording box with its own low power supply and data recording abilities. The fabric part will be new for each patient. The fabric part will be stored in a plastic sealed folder in the research room. Labelled with patients study number, in between scans. The plastic box part will be Clinicel wiped in between each patient. The device will be maintained by Kymira but training will be given to the staff at CUH.

Formatted: Superscript, Not Highlight

Formatted: Not Highlight

#### **8 SAFETY REPORTING**

#### 8.1 Definitions

## 8.1.1 Adverse Event (AE):

An AE or adverse event is:

Any untoward medical occurrence in a patient or other clinical investigation participant taking part in a trial of a medical device, which does not necessarily have to have a causal relationship with the device under investigation.

An AE can therefore be any unfavourable and unintended sign (including an abnormal laboratory finding), symptom or disease temporally associated with the use of the device, whether or not considered related to the device.

#### 8.1.2: Adverse Device Effect (ADE)

All untoward and unintended responses to the medical device.

The phrase "responses to a medical device" means that a causal relationship between the device under investigation and an AE is at least a reasonable possibility, i.e., the relationship cannot be ruled out.

All cases judged by either the reporting medically qualified professional or the sponsor as having a reasonable suspected causal relationship to the device qualifies as a device effect. For example, a rash at the site of contact with the fabric element of the device.

This also includes any event resulting from insufficiencies or inadequacies in the instruction for use or deployment of the device and includes any event that is a result of a user error.

## 8.1.3: Serious Adverse Event (SAE):

SAE is an adverse event that

- Led to death
- ♣ Led to fetal distress, fetal death or congenital abnormality or birth defect.
- Led to serious deterioration in the health of the subject that
  - Resulted in a life-threatening illness or injury
     NOTE: The term "life-threatening" in the definition of "serious" refers to an event in which the participant was at risk of death at the time of the event; it

CONFIDENTIAL

Page 14 of 29

Formatted: Superscript, Not Highlight

Formatted: Not Highlight

Formatted: Not Highlight

does not refer to an event which hypothetically might have caused death if it were more severe.

- Resulted in a permanent impairment of a body structure or a body function
- o Required in-patient hospitalisation or prolongation of existing hospitalisation
- Resulted in medical or surgical intervention to prevent permanent impairment to a body structure or a body function
- Other important medical events\*
   \*Other events that may not result in death, are not life threatening, or do not require hospitalisation, may be considered a serious adverse event when, based upon appropriate medical judgement, the event may jeopardise the patient and may require medical or surgical intervention to prevent one of the outcomes listed above

To ensure no confusion or misunderstanding of the difference between the terms "serious" and "severe", which are not synonymous, the following note of clarification is provided:

The term "severe" is often used to describe the intensity (severity) of a specific event (as in mild, moderate, or severe myocardial infarction); the event itself, however, may be of relatively minor medical significance (such as severe headache). This is not the same as "serious," which is based on patient/event outcome or action criteria usually associated with events that pose a threat to a participant's life or functioning. Seriousness (not severity) serves as a guide for defining regulatory reporting obligations.

#### 8.1.4: Serious Adverse Device Effects (SADE):

A serious adverse device effect (SADE) is any untoward medical occurrence seen in a patient that can be attributed wholly or partly to the device which resulted in any of the characteristics or led to a characteristics of a Serious adverse event.

SADE is also any event that may have led to these consequences if suitable action had not been taken or intervention had not been made or if circumstances has been less opportune.

All cases judged by either the reporting medically qualified professional or the sponsor.

## 8.1.5: Unanticipated Adverse Device Effect (UADE):

Any serious adverse device effect on health or safety or any life-threatening problem or death caused by, or associated with a device, if that effect, problem, or death was not previously identified in nature, severity or degree of incidence in the investigational plan or application (including a supplementary plan or application), or any other unanticipated

Version 2 April 12th 2021

serious problem associated with a device that related to the rights, safety or welfare of the subject.

#### 8.2 Reporting of AE

All AE's occurring during the study observed by the investigator or reported by the participant, whether or not attributed to the device under investigation will be recorded on the CRF as specified in the protocol. All ADE's will be recorded in the CRF.

The following information will be recorded: description, date of onset and end date, severity, assessment of relatedness to device, other suspect drug or device and action taken. Followup information should be provided as necessary.

The relationship of AEs to the device will be assessed by a medically qualified investigator or the sponsor/manufacturer and will be followed up until resolution or the event is considered stable.

All ADE that result in a participant's withdrawal from the study or are present at the end of the study, should be followed up until a satisfactory resolution occurs.

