# Formatted: Not Highlight Formatted: Superscript, Not Highlight Formatted: Not Highlight

## 2 SYNOPSIS

Study Title	WOMB: Wearable device to Observe Movements of your
	Baby (WOMB) study
	Baby (Weins) study
	An observational study to investigate the effectiveness and acceptability of a wearable smart garment to independently detect foetal movements in pregnant women
Internal ref. no.	
Type of study	Pre CE marking or Post Marketing Surveillance
Trial Design	Observational study
Trial Participants	Pregnant women weeks 32-38 of pregnancy
Planned Sample Size	54
Follow-up duration	24 weeks
Planned Trial Period	June-December 2021
Primary Objective	To determine the effectiveness of the wearable device in detecting fetal movements, as identified by the operator scanning, compared with those detected by the pregnant women.
Secondary Objectives	To determine the positive-predictive value of the wearable device in detecting foetal movements, compared with the pregnant women.     To establish the acceptability of the device for women
Primary Endpoint	The proportion of movements, as identified by the scan operator, that are successfully detected by the wearable device and the pregnant women (i.e., their sensitivity rates), at weeks 32, 34, 36, and 38 of pregnancy.
Secondary Endpoints	1. The proportion of movements detected by the device and by the pregnant women that are true-positives, that is those that are also identified by the scan operator (i.e., their positive-predictive value rates), at weeks 32, 34, 36, and 38 of pregnancy.  2. Acceptability of wearing the device as self-reported by the women in a bespoke end of study questionnaire.
Device Name	WOMB version 1 device
Manufacturer Name	Kymira
Principle intended use	A garment that can be worn to monitor fetal movements

Version 2 April 12th 2021

Formatted: Not Highlight

Formatted: Superscript, Not Highlight

Formatted: Not Highlight

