#### 8.3 Reporting Procedures for All SAEs/ SADEs/ UADEs

All SAE/SADE/UADEs need to be reported to the sponsor/legal representative and manufacture and CUH R&D immediately; regardless of relationship to the device.

All reporting to CUH R&D should give as much information about the incident as possible, and should be signed by the PI or Co-investigator.

The CUH R&D Department will undertake an initial review of the information. Events will be followed up until resolution, any appropriate further information will be sent by the research team in a timely manner.

Reporting to the MHRA will be done in liaison with the Chief Investigator and the Manufacturer.

The Manufacturer has a legal obligation to report all events that need to be reported to the Nominated Competent Authority immediately (without any unjustifiable delay) after a link is established between the event and the device, but no more than:

- ♣ 2 days following the awareness of the event for Serious Public Health Threat.
- 4 10 days following awareness of the event for Death or unanticipated serious deterioration in health.

CONFIDENTIAL

Formatted: Superscript, Not Highlight

Formatted: Not Highlight

Version 2 April 12th 2021

30 days following the awareness of the event for all other event meeting the SAE criteria.

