#### 9.1.3 Other Analyses

In addition to the analysis of the primary endpoint outlined above, an additional exploratory analysis may be conducted, pooling the data across visits and comparing the overall proportions of movements detected by the device compared with the mothers.

Summary statistics will be provided for subject demographics, medical history, and baseline measures.

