## 14 FINANCING AND INSURANCE

KYMIRA will provide funding for this study. The device under test is developed following IEC 62366, ISO 14971 and ISO 13485 for medical device safety, and IEC62304 for medical device software. Following and maintaining these standards is crucial as the proposed medical device product being developed will be classified under Class IIa as defined by the new medical device regulations (EU MDR 2017/745), and Class 2 under the USA's FDA 21 CFR Part 820.

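### Section 8.2 lets the sponsor/manufacturer alone assess device-relatedness, which leaves the either-party rule in 8.1.2 without a required clinical judgement

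*Protocol*

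**What the plan says.** Protocol Section 8.2 assigns the causality assessment: "The relationship of AEs to the device will be assessed by a medically qualified investigator or the sponsor/manufacturer". The medical qualification is attached to the investigator; none is stated for the alternative assessor.

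Section 8.1.2, which defines an adverse device effect (ADE), works differently. On which events meet that definition it says: "All cases judged by either the reporting medically qualified professional or the sponsor as having a reasonable suspected causal relationship to the device qualifies". Its example is "For example, a rash at the site of contact with the fabric element of the device".

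On the parties, the Synopsis has "Manufacturer Name Kymira" and Section 14 says "KYMIRA will provide funding for this study". Section 9.1.1 calls the study a pilot and the first test of this device on human subjects.

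Two safeguards do not depend on attribution. Section 8.2 requires all adverse events (AEs), "whether or not attributed to the device under investigation will be recorded on the CRF as specified in the protocol", and follows them until they resolve or are considered stable. Section 8.3 says that serious events "need to be reported to the sponsor/legal representative and manufacture and CUH R&D immediately; regardless of relationship to the device".

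**The concern.** The two sections share the word *or* but use it for different things. In 8.1.2 it makes the ADE definition inclusive: a positive view from either side is enough. In 8.2 it makes the assessment itself optional for one side, so that either party may supply it. Put together, the inclusive definition can be left without its clinical input.

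What is at stake is the classification of non-serious events. Serious events are reported whatever their attribution, so classification matters less there. For an event such as a contact rash, the relatedness entry decides whether it counts as a device effect. If that entry may come only from the company that makes the device and funds the study, any error is more likely to run towards too few ADEs.

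The protocol is more careful with the performance result. Section 6.1 blinds the scan operator to what the device detects and has the device data processed by a separate independent person. Section 8.2 has no comparable safeguard for relatedness.

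**Working it through.** The point rests on wording. The protocol states no ADE rate and no figure that depends on this rule, so there is nothing to reproduce or recompute. The check sets the sections side by side.

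**Step 1: who may assess (8.2).** A medically qualified investigator, or the sponsor/manufacturer. One is enough.

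**Step 2: what makes an event an ADE (8.1.2).** A judgement of related by the reporting medically qualified professional or by the sponsor.

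**Step 3: apply both rules to the possible combinations.**

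| Investigator's assessment | Sponsor/manufacturer's assessment | 8.2 satisfied? | ADE under 8.1.2? |
|---|---|---|---|
| Related | Related, not related or none | Yes | Yes |
| Not related | Related | Yes | Yes |
| Not related | Not related or none | Yes | No, and a clinician has judged it |
| None recorded | Related | Yes | Yes |
| None recorded | Not related | Yes | No, and no clinician has judged it |

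The table treats the sponsor and the manufacturer as one assessor, as 8.2 writes them.

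The first row shows that 8.1.2 does its job: a negative view from the company cannot cancel a positive clinical judgement. The last row is the gap. Section 8.2 is satisfied, the event is not an ADE, and the either-party rule has had no clinical judgement to act on.

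**Step 4: identify the interested party.** The Synopsis names the manufacturer and Section 14 names the funder; they are the same company. Whether that company is also the sponsor cannot be settled from the text: 8.2 joins the two with a slash, while 8.3 lists them separately. The gap does not depend on the answer, because 8.2 names the manufacturer explicitly.

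**Step 5: see what limits the consequence.** An event in the last row is still recorded on the case report form (CRF) with its description, dates, severity and relatedness (8.2). It is still followed to resolution or stability (8.2). If serious, it is reported immediately regardless of relationship, in a report that should be signed by the principal investigator or a co-investigator, and the hospital's R&D department makes an initial review (8.3). A progress/safety report goes to the ethics committee and R&D once a year or on request (8.4). What remains exposed is whether a non-serious event is labelled as device-related.

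**The case against.** The strongest reply is that assessment by the manufacturer alone is permitted by 8.2 but is neither required nor likely. Section 8.1.2 presupposes a reporting clinician who judges. AEs are those the investigator observes or the participant reports, so the investigator will normally know of them. Section 10 describes the device team as receiving anonymised device data. No section gives causality to the manufacturer alone. All this is fair, and it is why the point is minor. It does not remove the gap, because no sentence requires the clinician's relatedness judgement to be made or recorded.

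A reader might infer stronger things, which the documents do not support:

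- *That device harms could go unreported.* AEs are recorded whatever their attribution, and serious ones are reported regardless of relationship. The risk is misclassification of non-serious events.
- *That Section 9 omits safety.* Section 9.1.3 says only "Summary statistics will be provided for subject demographics, medical history, and baseline measures". A table of AEs or ADEs is commonly left to the statistical analysis plan, which is not at hand, so its absence here is no finding.
- *That an event classed as unrelated escapes follow-up.* Section 8.2 follows AEs until resolution or stability. For ADEs that lead to withdrawal or are present at study end, it asks for a satisfactory resolution, which is a limited difference in wording.
- *That the reporting clock starts only once a link is established.* That phrase in 8.3 concerns the manufacturer's reports to the competent authority, and the outer limits of 2, 10 and 30 days run from awareness of the event.
- *That the understatement can be quantified.* The protocol gives neither an ADE rate nor a share that would be misclassified, so any such figure would be an assumption.

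**Conclusion.** The concern holds in a limited form. Section 8.2 allows the sponsor/manufacturer alone to assess relatedness, the manufacturer funds this first-in-human study, and the rule does not fit the either-party definition in 8.1.2. Non-serious device effects could therefore be misclassified as unrelated, which would lower the ADE count.

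Severity is minor. The sensitivity, positive-predictive-value and acceptability analyses are untouched. The number of events affected cannot be estimated from the document, and it would be zero if an investigator in practice assesses every AE. The conclusion rests on the literal wording of 8.2 and on no other section requiring an investigator's relatedness assessment; none in the protocol does.

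**What to change.** Reconcile 8.2 with 8.1.2. State in 8.2 that a medically qualified investigator's relatedness assessment is recorded for every AE, that any sponsor/manufacturer assessment is made in addition to it and not in its place, and that an event counts as an ADE if either judges it related. The manufacturer's view can then add an event to the ADE count but cannot be the only basis for leaving one out. Use the same names for the parties in 8.1.2 and 8.2, since one says sponsor and the other sponsor/manufacturer.

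The cost is about one sentence. Relatedness is already among the items recorded for each AE, and the investigators are in place. If both assessments are to be kept apart, the CRF needs to show who made each. The downside is a possibly higher ADE count. No analysis or sample size changes.
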